Demographics medical history including historical creatinine data, baseline conditions.	X	X												
Check of in-/exclusion criteria	X													
Background ³ therapies (e.g. ACEis, ARBs and SGLT2)	X	X			X			X			X			X
Height	X													
Weight	X													
Physical examination	X	X			X			X			X			X
Vital signs	X	X			X			X			X			X
Optional biobanking sampling (serum, plasma, urine)		X												
First Morning Void Urine ⁴		X												X

Proprietary confidential information © 2022 Boehringer Ingelheim International GmbH or one or more of its affiliated companies

Trial Periods	Screening	Prospective Period												
		1	2	3	4	5	6	7	8	9	10	11	12	13
Sampling at Home and Clinic visits	1	2	3	4	5	6	7	8	9	10	11	12	13	14
Weeks	Screening ¹ -2 to 0	Baseline 1	4	8	12	16	20	24	28	32	36	40	44	48/ EOT
Days	-14 to 0	1	28	56	84	112	140	168	196	224	252	280	308	336
Permitted visit window (days)	-	0	± 4	± 4	± 4	± 4	± 4	± 4	± 4	± 4	± 4	± 4	± 4	± 4
Train patient on Urine and Mitra [®] sampling ⁵	X													
Provide Home sampling kits (for Urine and Mitra [®] Cartridges)		X			X			X			X			
Mitra [®] micro sampling at home ⁶			X	X		X	X		X	X		X	X	
Mitra [®] micro sampling at clinic visits		X			X			X			X			X
Provide training on smartphone/ tablet application including provision of app /device ⁷		X			X			X			X			
Mitra [®] micro sampling at Home paper diary handout (where electronic capture is not used)		X			X			X			X			
Review of home Mitra [®] sampling and Urine via application or paper diary (to be collected)					X			X			X			X
eGFR (central laboratory) ⁸	X	X			X			X			X			X
Safety laboratory		X			X			X			X			X

[figure not shown]
Proprietary confidential information © 2022 Boehringer Ingelheim International GmbH or one or more of its affiliated companies

Trial Periods	Screening	Prospective Period												
Sampling at Home and Clinic visits	1	2	3	4	5	6	7	8	9	10	11	12	13	14
Weeks	Screening ¹ -2 to 0	Baseline 1	4	8	12	16	20	24	28	32	36	40	44	48/ EOT
Days	-14 to 0	1	28	56	84	112	140	168	196	224	252	280	308	336
Permitted visit window (days)	-	0	± 4	± 4	± 4	± 4	± 4	± 4	± 4	± 4	± 4	± 4	± 4	± 4
All AEs/SAEs	X	X			X			X			X			X
Completion of patient participation														X

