3. DESCRIPTION OF DESIGN AND TRIAL POPULATION

3.1 OVERALL TRIAL DESIGN

This trial is a multicentre, non-randomized, low-intervention trial that does not involve administration of study drug and includes both a retrospective and prospective phase in patients with chronic kidney disease who are on stable background treatment according to respective local guidelines.

The trial targets to enrol at least 33% (up to 60%) of non DKD patients; the remaining patients will consist of DKD patients.

[figure not shown]
In this study, eGFR slopes will be calculated from historically available creatinine values (retrospective phase of study) that were collected during routine clinical care of the patients prior to enrolment in this study. In the prospective phase of the study, creatinine values will be systematically collected at predefined time points. The eGFR slopes will then be calculated from the retrospective and prospective phases.

A schematic illustration of the trial design is presented in Figure 3.1: 1.

Retrospective phase: At least 4 Serum Creatinine measurements at minimum. However, it is desirable to have as many as available.

Prospective phase: 48 weeks duration.

Site visits – Blood sample collection at baseline and every 12 weeks (i.e. Week 12, Week 24, Week 36, Week 48). Urine sample collection (for UACR determination) at baseline and Week 48. At home (using Mitra® Device) blood samples will be collected on a biweekly basis for the first 12 weeks and thereafter on a 4-weekly basis until Week 48. If site visit coincides, Mitra® device sample will be collected in combination with venous sample on site.

* Screening period of up to 2 weeks between retrospective and prospective phases.

Baseline visit is considered as Visit 2/Day1 of prospective phase

Figure 3.1: 1 Trial design

Patients will be screened in the trial once they have signed the informed consent. They will undergo a screening period of up to 2 weeks from the time of informed consent. All available historical eGFR values, UACR/PCR within the 5.5 years prior to screening Visit 1 will be

collected for each patient. Patients who successfully complete the screening and meet the inclusion / exclusion criteria, including the availability of requisite historical eGFR data, will qualify for enrollment into the 48 weeks prospective phase of the study (see [Figure 3.1: 1](#)).

Retrospective phase:

To be documented in the CRF:

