- All available serum creatinine values (at least 4 serum creatinine values should be available for a patient with the most recent creatinine value not more than 6 months prior to Visit 1 (Screening Visit). The most recent and oldest serum creatinine values should be no less than 1 year apart and no greater than 5 years apart and there should be no gap of creatinine values of 2 years or longer.
- All available UACR values or respective values to determine UACR.
- All available PCR values or respective values to determine PCR.
- Medications that could potentially have an impact on calculation of slopes during the retrospective phase e.g. ACEi/ARB.
- Medical history as outlined in the CRF.

Prospective Phase:

The serum eGFR and UACR value obtained at the Baseline Visit will be used as the first eGFR and UACR value. The prospective eGFR slope (i.e. the individual rate of eGFR decline) will be established over 48 weeks, during which time the patient will be on background optimal standard of care. Patients need to attend the investigational site in person six times during the study (at Screening Visit, baseline visit, 12 weeks, 24 weeks, 36 weeks and 48 weeks visit) for venous blood samples, and collection of data with regards to the patients' current treatments and other medications. In order to minimize the number of visits required, all other eGFR values will be calculated from the finger prick blood samples taken at home using the Mitra[®] micro sampling device during the prospective phase of the study. Mitra[®] samples taken at home between visits will be shipped by the patient to the central laboratory or the site, if allowed by local regulations. Where this is not possible alternative arrangements will be made, e.g. samples taken to the investigational site. Samples taken directly prior to a physical visit will be taken to the site to be processed by the site staff. To allow a comparison of the patient kits with conventional collection methods, sites will use the Mitra[®] kits to process samples in parallel to the collection of a certain volume of blood. Both serum and Mitra[®] measurements will form the basis for the eGFR slope calculation.

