5.2.3 Safety laboratory parameters

Safety laboratory parameters to be assessed are listed in [Table 5.2.3: 1](#). For the sampling time points please see the flow chart.

A central laboratory result will be used to confirm eGFR for eligibility; the respective reference ranges will be provided in the ISF.

To ensure sufficient hydration, patients should be strongly encouraged to come not fasted to their study visits.

Instructions regarding sample collection, sample handling/ processing and sample shipping are provided in the Laboratory Manual in the ISF. Where samples are collected by the patient directly, appropriate instructions in lay language will be provided.

The central laboratory will provide reports to the investigator. It is the responsibility of the investigator to evaluate the laboratory reports. Clinically relevant abnormal findings as judged by the investigator will be reported as adverse events (please refer to [section 5.2.6](#)).

Lab tests may need to be repeated in case of required medical follow-up due to an adverse event or if a test was not successful due to incorrect specimen handling or storage.

To test the eGFR throughout the trial, the site will collect a small capillary blood volume from the patient with the Mitra[®] tool at visits indicated in the [flow chart](#). The Mitra[®] tool will also allow the patient to collect blood at home. Therefore, at home patients will need to collect one blood sample on their own (one Mitra[®] cartridge with two sampling tips) and ship them to the central lab or the site, if permitted by local legislation. Alternatively, the patient will need to take the specimens to the site directly.

The central laboratory will transfer the results of the analysis to the CRO.

The CKD-EPI Equation is used for reporting eGFR based on serum creatinine (see [appendix section 10.2](#)).

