#### 4.10.2 Primary Outcome Variable

The primary outcome is the homogeneity (eGFR slope shift table) between eGFR slopes derived from retrospective and prospective eGFR values. All analyses of the primary outcome will be done on the FAS, and percentages will be based on the number of patients in the FAS, unless otherwise specified.

Retrospective and prospective eGFR slopes will be derived using a linear random slope model. The prospective eGFR slope for each patient will be derived using eGFR values in the prospective phase as the dependent variable and time in the prospective phase (years, starting from baseline) as the continuous independent variable with random intercept and random slope. The retrospective eGFR slope for each patient will be derived similarly using the data in the retrospective phase, and time in the retrospective phase will be calculated relative to the first retrospective measurement per patient. Note that for the prospective slope, all measurements from baseline until the last available visit will be considered for inclusion in the estimation, including unscheduled visits.

The primary analysis assessing homogeneity between retrospective and prospective eGFR slopes will first be performed using the retrospective eGFR slopes collected from retrospective data, and the prospective eGFR slopes derived using prospective eGFR measurements from Mitra® samples from both at-home and clinic visits. The primary analysis will then be performed again using the retrospective eGFR slopes collected from retrospective data, and prospective eGFR slopes derived from prospective eGFR measurements from venous blood samples from clinic visits. This is in order to assess differences in the slope estimation depending on the data source.

Other than this requirement, all available patient data will be included for the estimation of the retrospective slope. However, for the prospective slope, the following additional data resulting from changes to background therapy will be excluded from the eGFR slope estimation:

- For patients on SGLT2i/ACEi/ARB background therapy at date of eGFR baseline measurement, eGFR data collected after the patient dropped out of SGLT2i/ACEi/ARB will be excluded
- For patients who are not on SGLT2i/ACEi/ARB background therapy at date of eGFR baseline measurement, eGFR data collected after the patient starts SGLT2i/ACEi/ARB will be excluded

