**Equation 1**

$$E(Y_{ij}) = a_0 + b_{0j} + (a_1 + b_{1j})T_{ij}$$

Where  $a_0$  is the fixed effect term for the common intercept (across all patients),  $b_{0j}$  is the term for the random intercept of patient  $j$  and follows a Normal distribution,  $a_1$  is the fixed effect term for the common slope (across all patients) and  $b_{1j}$  is the term for the random slope of patient  $j$  and follows a Normal distribution.  $T_{ij}$  represents the time (in years) in the phase for patient  $j$  and time  $i$ . For a given patient, the random slope quantifies the difference between the observed eGFR slope of the patient and the population-averaged (common) eGFR slope. Therefore the combination of  $a_1 + b_{1j}$  represents the eGFR slope for each patient, and will be the primary quantity of interest in this analysis. The primary analysis will come from an unadjusted model as shown above. An autoregressive covariance structure will be used in this model in the first instance, however other covariance structures may be used, especially in the case of model non-convergence. If an autoregressive covariance structure results in non-convergence, then a compound symmetry structure will be tried. In the case that neither of these covariance structures results in convergence, other structures may be tried and the final choice of covariance structure will be detailed in the output. Note that the eGFR slope resulting from Equation 1 is expected to be negative as eGFR is expected to decline over time.

[figure not shown]
The primary analysis used to evaluate homogeneity of the slopes will be a shift table of the shift in number of patients with categories of estimated eGFR slopes of  $> -1$ ,  $> -3$  to  $-1$  (slow progression) and  $\leq -3$  mL/min/1.73m^2/year (fast progression) from the retrospective phase to the prospective phase. This analysis will be presented overall and for the DKD and non-DKD populations. Percentages will be based on the number of patients within each category in the retrospective phase. This analysis will

[figure not shown]
be performed once using prospective eGFR measurements from Mitra® samples and once using prospective eGFR measurements from venous blood samples.

[figure not shown]

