#### 4.11.2 Clinical Laboratory Evaluation

The analyses of laboratory data will be descriptive in nature. Analyses will be based on SI units and on standardized values for all parameters except urine albumin, urine protein, urine creatinine, UACR and PCR, which will be reported in the conventional units. Results from the central laboratory will be included in the reporting of this study for the following laboratory groups:

- Hematology
- Chemistry
- Urine Chemistry.

Laboratory parameters will be collected at the following visits, as per the CTP (for all parameters except eGFR collected at home via Mitra® micro sampling):

- Baseline (visit 2)
- Visit 5
- Visit 8
- Visit 11
- Visit 14 (end of study visit).

For eGFR collected at home via Mitra® micro sampling, these will additionally be collected at visits 3, 4, 6, 7, 9, 10, 12, 13 and will be collected bi-weekly at visits 2, 3 and 4.

For by-visit summaries, the last non-missing assessment (including repeat assessments) recorded at each visit will be summarized. In the case that there are multiple measurements taken on the same date and time, and these measurements are simultaneously the last non-missing assessment at a visit, then the mean of these measurements will be taken and this average will be used in the analysis. Unscheduled visits will not be included in the summary tables. Listings will present all visits, including unscheduled ones.

At each visit, laboratory measurements will be compared with the relevant laboratory reference ranges and categorized as abnormal (low/high) or normal:

- Low: below the lower limit of the laboratory reference range
- Normal: within the laboratory reference range (upper and lower limit included)

- High: above the upper limit of the laboratory reference range.

Descriptive summaries of the baseline, post-baseline and change from baseline in laboratory parameters will be presented by laboratory parameter and visit. Additionally, a summary of the number and percentage of patients with abnormal laboratory values will be presented by laboratory parameter and visit. Percentages will be based on the number of patients with a measurement at the visit (per parameter).

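### The Mitra run pools home and clinic samples with no term for place of sampling; under the biweekly schedule a systematic home-clinic difference, if there is one, would bias slopes by an amount that depends on follow-up

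*SAP*

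**What the plan says.** SAP 4.10.2 performs the primary analysis twice. The first run takes prospective slopes from Mitra "samples from both at-home and clinic visits". The second takes them from clinic venous samples, so that the two data sources can be compared. Equation 1 contains an intercept, time, and a random intercept and slope per patient. The SAP adds: "The primary analysis will come from an unadjusted model as shown above".

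Protocol 5.2.3 separates who takes the sample. At visits, "the site will collect a small capillary blood volume from the patient"; at home, patients do it themselves. Protocol 1.4.2 also allows a caregiver.

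On timing, Protocol 3.1 says that home "blood samples will be collected on a biweekly basis for the first 12 weeks and thereafter on a 4-weekly basis until Week 48". Flow chart footnote 6, Protocol 1.4.2 and the notes to SAP Figure 3.1:1 agree. SAP 4.11.2 likewise says that home samples "will be collected bi-weekly at visits 2, 3 and 4". The flow chart row for Mitra "micro sampling at home" marks only 4-weekly visits; the extra biweekly samples appear only in its footnote. Clinic Mitra samples fall at baseline and Weeks 12, 24, 36 and 48.

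Parallel Mitra and venous sampling is done by sites at visits: "To allow a comparison of the patient kits with conventional collection methods".

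**The concern.** A linear slope is sensitive to any measurement shift that is associated with time. If home samples read systematically higher or lower than site-taken ones, for example through finger-prick technique or handling, and home samples cluster early, Equation 1 has nowhere to put the difference except the time coefficient. An offset shared by patients falls on the common slope a1, so the random effects do not absorb it.

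The result is a shift table cut at -1 and -3, with a slow band only 2 units wide. A shifted prospective slope moves patients across those cuts and can be read as poor agreement with the retrospective slope. The Mitra-venous pairs do not reveal such an offset, because every pair is taken at the clinic.

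**Working it through.** **The plan's own figure.** The only numeric design statement is that 600 patients give an estimate of at least 67% (true value 70%) or 47% (true value 50%) with probability 95%. The bound p - 1.645 x sqrt(p(1-p)/600) gives 66.9% and 46.6%, so it reproduces. The present point does not depend on it.

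**Inputs.**
- Clinic Mitra weeks: 0, 12, 24, 36, 48 (mean 24).
- Home weeks under the biweekly text: 2, 4, 6, 8, 10, 16, 20, 28, 32, 40, 44 (mean 19.1).
- Home weeks on the flow chart columns alone: 4, 8, 16, 20, 28, 32, 40, 44 (mean 24).
- d, the home-minus-clinic difference in eGFR: not in the documents. An assumed range of 1 to 5 mL/min/1.73m² is shown.

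**Formula.** The slope bias per unit of d is the least-squares slope of a home indicator h on time: Σ(t - t̄)h / Σ(t - t̄)².

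**Completer, biweekly schedule (16 samples, mean week 20.625).**
- -16.875 / 3733.75 = -0.00452 per week; x 52.18 = **-0.236 per year per unit of d**.
- Random intercept and slope weights with independent errors leave this unchanged.
- With autoregressive errors (assumed correlation 0.2 to 0.8) it is between -0.23 and -0.04.
- For d = 1, 2, 3, 4, 5 the bias is -0.24, -0.47, -0.71, -0.94, -1.18 (independent errors). A 1-unit shift in slope needs d of 1/0.236 = 4.2.

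**Completer, flow chart columns only.** Home and clinic means are both Week 24, so the bias is 0. The ±4-day windows move it by at most about 0.04 per unit.

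**Truncated follow-up, biweekly schedule.** Patient-level least squares, using all planned samples up to the last week of data:

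| Last week | 12 | 16 | 20 | 24 | 28 | 32 | 36 | 40 | 44 | 48 |
|---|---|---|---|---|---|---|---|---|---|---|
| Bias per unit of d | 0.00 | +0.65 | +0.81 | -0.51 | -0.03 | +0.19 | -0.34 | -0.09 | +0.06 | -0.24 |

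The sign depends on whether the last sample was taken at home or at the clinic. For example, data to Week 20 plus an assumed closing clinic sample at Week 22 give -0.41 instead of +0.81.

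**Illustration on the shift table.** Assume true prospective slopes with mean -4 and SD 3, and all patients completers. The share at or below -3 is 63%; it becomes 69% for d = +2 and 57% for d = -2.

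**Price of a home/clinic term.** With complete sampling, r² between the indicator and time is 0.022. The variance inflation is 1/(1 - 0.022) = 1.023, and the standard error rises by about 1.1%. If home sampling stopped after Week 20 while clinic visits continued, the variance inflation is 1.37 and the standard error rises by about 17%.

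**The case against.** The strongest objection is that nothing shows d to be other than zero. The documents describe one device, one central laboratory, a validated method with stability for up to three months, and patient training at screening. Protocol 5.1.1 has the cartridge shipped to the central laboratory without limiting this to home samples, so transport is not clearly a home-only feature. This stands: the point is a risk.

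A reader might infer that any home-clinic difference becomes a false slope in every patient, in one direction. The documents do not support that. The study was terminated in July 2022 (SAP 3.1.1.1), the FAS needs only one post-baseline assessment (SAP 4.6), and prospective data stop at a background-therapy change (SAP 4.10.2). Truncated patients carry biases of either sign, some near zero, and these partly offset in the common slope.

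A reader might also reach for larger figures: -0.63 per unit if the Week 40 and 44 home samples are missing, or -0.96 if home sampling stops after Week 20. Both assume that every clinic visit to Week 48 is kept, a pattern that the documents do not describe. Losing early home samples does the opposite: without Weeks 2 and 4 the figure is -0.07.

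The venous run contains no home samples and cannot carry this bias, so homogeneity does not rest on Mitra alone. That also stands. But the venous run changes matrix, assay and number of samples (5 instead of 16) at once, so a disagreement between the runs could not be attributed to place of sampling.

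Finally, SAP 4.10.1.1 refers to supportive analyses in section 4.10.2.2, which is not visible. An adjusted analysis may exist there; only the primary model is known to be unadjusted.

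**Conclusion.** The point holds as a cheap improvement against a possible bias. Under the biweekly schedule, a constant difference d biases a completer's Mitra slope by about -0.24 x d per year with independent errors, less with autoregressive errors (the SAP's first choice of covariance structure). For truncated patients the range is about -0.5 to +0.8 per unit of d. Bias that varies with length of follow-up still distorts a shift table, but it is not a uniform displacement of all patients.

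This rests on an additive d that is constant over time and across patients, on the planned sampling weeks, and on the biweekly text. On the flow chart columns alone the completer bias is zero. With d of 1 unit the effect on a completer is small against the 2-unit slow band; it becomes material at around 4 units. The documents do not say which, if either, applies. The study is exploratory with no formal hypothesis, which also limits the weight of the point.

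**What to change.** - In the Mitra run, add one fixed effect to Equation 1 for place of sampling (home or clinic) and report its estimate with a confidence interval. A constant d then causes no slope bias at any length of follow-up. A difference that varies between patients is removed only on average.
- Show the clinic-only Mitra slope as a sensitivity check. It shares the assay with the main Mitra run and the visit times with the venous run, so it helps to locate a disagreement. It is less precise: the time sum of squares is 1440 instead of 3733.75, so a completer's slope standard error is sqrt(3733.75/1440) = 1.6 times as large at equal residual variance. It should therefore not replace the pooled run.
- Reconcile the flow chart columns with footnote 6 and the text on home sampling times.
- If section 4.10.2.2 already contains such an analysis, a cross-reference is enough.

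The cost is one SAP sentence, one model term and one extra output, all from data already collected. The slope standard error rises by about 1% with complete sampling, and by up to about 17% if home sampling stops after Week 20.

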**Figure 3.1:1 Trial design**

**Retrospective phase:** At least 4 Serum Creatinine measurements at minimum. However, it is desirable to have as many as available.

**Prospective phase:** 48 weeks duration. Site visits – Blood sample collection at baseline and every 12 weeks (i.e. Week 12, Week 24, Week 36, Week 48). Urine sample collection (for UACR determination) at baseline and Week 48. At home (using Mitra® Device) blood samples will be collected on a biweekly basis for the first 12 weeks and thereafter on a 4-weekly basis until Week 48. If site visit coincides, Mitra® device sample will be collected in combination with venous sample on site.

\* Screening period of up to 2 weeks between retrospective and prospective phases.

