Summary statistics (mean, SD, min, median, max) of the estimated eGFR slopes will be presented by phase, for the overall population and for the DKD and non-DKD populations, and this analysis will be performed once using prospective eGFR measurements from Mitra® samples and once using prospective eGFR measurements from venous blood samples.

To aid in assessing the reliability of the slope estimation, the residual variance (i.e. mean squared error) of the slope estimates will also be presented for both the retrospective and prospective slopes, and this residual variance will be estimated from the linear random slope model in [Equation 1](#).

A by-patient listing of the primary outcome data will be provided including patient identifier, site, country, age, sex, race, patient population (DKD/non-DKD), phase of measurement (retrospective/prospective), visit, date of baseline, sample collection/assessment day, indicator of whether sample was taken and reason not done (for prospective eGFR only), name of formula used to calculate eGFR, eGFR measurement, and indication of whether paper diary was reviewed (at clinic visits in prospective phase only), and data source (Mitra®/venous blood) for prospective phase. Note that the assessment day will be calculated relative to baseline. Data from all visits (including unscheduled visits) will be listed, and data collected 4 weeks before AKI and up to 8 weeks after the AKI (which were excluded from the analysis) will be listed and marked with [AKI] in the listing. Data excluded from the primary analysis due to changes in background therapy will be marked with [BAC] in the listing.

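### The Mitra and venous primary runs are compared to show the effect of data source, but they also differ in sampling density, timing and setting, so a difference between them cannot be put down to sample type alone

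*SAP*

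**What the plan says.** SAP 4.10.2 specifies two versions of the primary analysis against the same retrospective slopes. The first uses "prospective eGFR measurements from Mitra® samples from both at-home and clinic visits". The second uses "prospective eGFR measurements from venous blood samples from clinic visits". The stated purpose is: "This is in order to assess differences in the slope estimation depending on the data source". The listing description later in 4.10.2 shows what the term covers, since each prospective value is tagged by "data source (Mitra®/venous blood) for prospective phase". Data source therefore means sample type.

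The window for the prospective slope opens at baseline ("all measurements from baseline until the last available visit will be considered for inclusion in the estimation"), so the screening venous sample does not count. For Mitra, SAP Figure 3.1:1 says that "blood samples will be collected on a biweekly basis for the first 12 weeks and thereafter on a 4-weekly basis until Week 48", and Protocol 3.1 agrees. SAP 4.11.2 places the extra samples by saying that home Mitra samples "will be collected bi-weekly at visits 2, 3 and 4". Venous blood for creatinine is taken at baseline and weeks 12, 24, 36 and 48. Mitra samples are also taken at those five visits. Protocol 3.1 says this parallel sampling is there so that the patient kits can be compared with conventional collection.

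The quantity put into categories is the patient-specific slope from the random-slope model, with an autoregressive covariance structure tried first. The study is exploratory, with no formal hypothesis testing.

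**The concern.** The two runs differ in more than sample type. The Mitra run has more time points, clusters them in the first 12 weeks, includes self-collected home samples, and depends on which shipped samples give a result. The venous run has five evenly spaced clinic samples.

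This matters because a model-based patient slope is pulled toward the cohort mean, and the pull is stronger when the patient contributes less information. Fewer samples narrow the distribution of predicted slopes, and a narrower distribution puts different shares of patients on either side of −3 and −1. A gap between the two shift tables could thus appear with no assay difference, and a real assay difference could be exaggerated, hidden or reversed. Since the comparison by data source is the stated reason for running the primary analysis twice, its result needs to be interpretable.

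**Working it through.** The documents give no figure for the Mitra–venous comparison. The SAP 4.12 precision statement for 600 patients reproduces (exact binomial probabilities 0.949 for 70%/67% and 0.935 for 50%/47%) and is not affected by this point.

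**1. Time points from baseline.**
- Mitra: weeks 0, 2, 4, 6, 8, 10, 12, 16, 20, 24, 28, 32, 36, 40, 44, 48, which is 16.
- Venous: weeks 0, 12, 24, 36, 48, which is 5.
- The flow-chart columns alone, without the biweekly footnote, give 13 for Mitra.

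**2. Slope precision, independent errors of equal SD σ.** SE = σ/√Sxx, where Sxx is the sum of squared deviations of time from its mean.
- Mitra: mean week 20.625, Sxx = 3733.75 weeks² = 1.371 years², SE = 0.854σ.
- Venous: mean week 24, Sxx = 1440 weeks² = 0.529 years², SE = 1.375σ.
- Ratio: √(3733.75/1440) = √2.593 = 1.61. With 13 Mitra points: √(2912/1440) = 1.42.

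**3. Share classed fast when the assays are identical.** Let τ be the true slope SD and μ the cohort mean. If the intercept carries no information on the slope, reliability is R = τ²/(τ² + SE²), predicted slopes have mean μ and SD τ√R, and the share at or below −3 is Φ((−3 − μ)/(τ√R)).

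Example, τ = 2, σ = 3, μ = −4:
- Mitra: SE = 2.56, R = 4/(4 + 6.56) = 0.379, SD = 1.23, share = Φ(1/1.23) = 79.2%.
- Venous: SE = 4.13, R = 4/(4 + 17.02) = 0.190, SD = 0.87, share = Φ(1/0.87) = 87.4%.

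All four assumed settings at μ = −4 (gaps from unrounded values):

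| τ | σ | Predicted-slope SD, Mitra / venous | % fast, Mitra / venous | Gap |
|---|---|---|---|---|
| 2 | 3 | 1.23 / 0.87 | 79.2 / 87.4 | 8.2 |
| 2 | 4 | 1.01 / 0.68 | 83.9 / 92.8 | 8.9 |
| 3 | 3 | 2.28 / 1.76 | 66.9 / 71.5 | 4.5 |
| 3 | 4 | 1.98 / 1.44 | 69.3 / 75.7 | 6.4 |

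**4. Dependence on the cohort mean.** The gap is 2.5 to 7.8 points at μ = −3.5. It is exactly 0 at μ = −3, because the cut-off then sits at the centre of both distributions. At μ = −2 it is −4.5 to −8.9 points. A zero gap in the fast share does not make the tables equal: at μ = −3, τ = 2, σ = 3, the share above −1 is 1 − Φ(2/1.23) = 5.2% with Mitra and 1 − Φ(2/0.87) = 1.1% with venous.

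**5. Dependence on autocorrelation.** Take residuals with correlation ρ at a 4-week lag, decaying as ρ^(weeks/4), and generalised least squares:

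| ρ | SE/σ, Mitra / venous | Ratio | Gap at μ = −4 |
|---|---|---|---|
| 0 | 0.854 / 1.375 | 1.61 | 4.5 to 8.9 |
| 0.3 | 1.184 / 1.390 | 1.17 | 1.9 to 3.0 |
| 0.6 | 1.423 / 1.468 | 1.03 | at most 0.6 |

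At ρ = 0.8 the SE ratio is 1.003.

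**6. Simulation of the SAP model.** Settings: identical assays, independent errors, two-thirds of patients enrolled as fast and one-third as slow by retrospective slope, population mean −3 to −4, slope SD 2–4, residual SD 3–8. With 5 samples, the overall fast share was 6–15 points higher and slow-to-slow 9–18 points lower than with 16. The zero-gap case does not arise here because 57–69% of those enrolled were truly fast.

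**7. Matched visits.** With Mitra limited to the five clinic visits, both runs have SE = 1.375σ, and the simulated tables agree within about 2 points. At mean −3.5, slope SD 3 and residual SD 5, fast-to-fast is 93.6% versus 93.7%, against 87.9% with 16 Mitra samples.

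**The case against.** The strongest reply is that the size of the artefact is not known. Cohort mean, slope SD, error SD and autocorrelation are all absent from the documents. The gap in the fast share vanishes at a mean of −3, reverses at −2, and nearly disappears under strong residual autocorrelation. The SAP itself names an autoregressive structure first, though it does not say whether this applies to the residuals or to the random effects. This stands. A reader might infer that the venous run will class several points more patients as fast; the documents support neither that direction nor that size.

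Second, the SAP describes openly what goes into each run, sets no decision rule and tests nothing between them. Comparing each data stream in full, as it would be used, is legitimate when choosing between sampling strategies, and Protocol 7.2.2 does speak of choosing the most appropriate data by residual variance. A reader might infer that the plan commits to an assay-only conclusion; it does not. But the stated purpose is a difference by data source, and the SAP's own label for that is sample type.

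Third, slope summary statistics are given for each run, and sampling density alone does not bias the mean slope. A systematic source effect on mean decline could be seen there. That helps for the mean but not for the shift table, which is the primary analysis.

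Fourth, a reader might infer that no paired comparison is planned anywhere. That cannot be asserted. Objectives after the primary one are blacked out, SAP 4.10.2.2 and 4.10.3.2 are cited but not visible, and Protocol 3.1 declares an intention to compare the kits. What can be said is that the visible primary-analysis text has neither a matched run nor a caveat.

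Last, matching does not remove all patient-level disagreement. Under assumed mean −4, slope SD 2–3, total error SD 3–4 and part of the error shared between paired samples, category disagreement is 16–33% as planned and 7–28% at matched visits.

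**Conclusion.** The point holds as one of interpretation. As planned, the Mitra and venous shift tables differ in sample type, density, timing, setting and availability of results, and the visible text offers no way to separate these. The schedule counts (16 and 5) come from the documents. The SE ratio of 1.61 follows from them if errors are independent with equal SD.

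The effect on classification rests on assumptions. With slope SD 2–3, error SD 3–4 and independent errors, the venous run differs in the fast share by +4 to +9 points at a mean of −4, 0 at −3, and −4 to −9 at −2. At a mean of −4 it is about 2–3 points with a 4-week residual correlation of 0.3, and under 1 point at 0.6. Size and direction are therefore uncertain. After the July 2022 termination, many patients may also have fewer samples than scheduled. Because the study is exploratory, the consequence is a misread secondary conclusion about data source, not an invalid test.

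**What to change.** Keep both planned runs. In SAP 4.10.2 add a matched supportive pair: Mitra results from clinic visits only, and venous results, both limited to the same patients and visits with a valid result of each type, and fitted with the same covariance structure. If one model of the pair needs a fallback structure, use it for both. State that differences are attributed to sample type only from this pair, and that full Mitra against clinic-only Mitra is read as the effect of the added home sampling. To keep that second contrast clean, also note how many patients and visits drop out through matching.

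The cost is two more model runs with their shift tables, on data already collected. The matched set is a subset of the FAS with at most five points per patient, so its slopes are strongly shrunken, and some patient-level disagreement from measurement error will remain between equally good assays. If a redacted section already contains a paired slope comparison, it is enough for 4.10.2 to refer to it for the data-source conclusion.
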